Informed written consent (appendix 3) will be obtained prior to enrolment on study. In the case of Adults Lacking in Capacity (ALC), and where a family member is not available to act as a nominated person the research team in conjunction with the PI will identify a nominated person who is unrelated to the conduct of the research and willing to provide a declaration for this study. The nominated person will always be a member of the nursing/medical staff or the management team and part of the wider multi-disciplinary team within the hospital ward or nursing home facility of the individual lacking capacity. They (the nominated person) will also be provided with an invitation letter and PIS (appendix 11) and any queries answered, the nominated person can then contact the research team if they think the potential participant would have been interested in this research. The potential participant will not be enrolled on the study until full informed consent (appendix 12) has been given by the nominated person.

Rapid Access to retrospective samples from nasopharyngeal swabs

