identify a nominated responsible person who is unrelated to the conduct of the research and willing to provide a declaration for this study. The nominated person will always be a member of the nursing/medical staff or the management team and part of the wider multi-disciplinary team within the hospital ward or nursing home facility of the individual lacking capacity. They (the nominated responsible person) will also be provided with an invitation letter and PIS (appendix 11) and any queries answered, the nominated person can then contact the research team if they think the potential participant would have been interested in this research. The potential participant will not be enrolled on the study until full informed consent (appendix 12) has been given by the nominated person. This will still apply at all time points for those individuals who are unlikely to regain capacity and for those patients in hospital who are sedated/ventilated due to their COVID-19 symptoms, who may regain capacity. For those patients, capacity will always be assessed by a member of their direct clinical care team, the nurse in charge/manager in the nursing home and the PI at each hospital site who will be the consultant on or linked to the COVID ward (**The person assessing capacity will be recorded at all time points and a record kept**). For those that regain capacity during the duration of this research they will be given participant information sheet (appendix 4) to read for themselves and their consent (appendix 5) will be sought if they wish to proceed with the study. If they do not wish to continue, they will be given the option for any samples and data to be withdrawn and destroyed.

Hospital and nursing home patient recruitment:

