COVID-19 positive/ SARS-CoV-2 inpatients and non-hospitalised patients (n = 700) aged 18 years and over tested at the WHSCT, BHSCT and SHSCT and have been admitted to COVID-19/ SARS-CoV-2 hospital wards (including from the Intensive Care Units) or out-patient and residents of trust affiliated nursing homes will initially be approached by their clinician, senior nurse or an NICRN research nurse. They will speak to the patient(s) about the study and if the patient is interested, verbal consent will be gained for the researcher to follow up with a Participant Information sheet (PIS) (appendix 6). Those interested patients fulfilling the inclusion criteria can then speak directly face to face (whereby the nurse will arrange a convenient time for researcher to visit the patient) to the researchers, the study will be discussed in detail and any issues will be addressed. If they are still interested in participating, written informed consent (appendix 7) will be obtained from the patient by the researcher(s) prior to enrolment on the study.

In the case of those ALC, and where a family member is not available to act as a nominated person the research team in conjunction with the PI will identify a nominated person who is unrelated to the conduct of the research and willing to provide a declaration for this study. The nominated person will always be a member of the nursing staff or the management team and part of the wider multi-disciplinary team within the hospital ward or nursing home facility of the individual lacking capacity. They (the nominated person) will also be provided

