with an invitation letter and PIS (appendix 13) and any queries answered, the nominated person can then contact the research team if they think the potential participant would have been interested in this research. The potential participant will not be enrolled on the study until full informed consent (appendix 14) has been given by the nominated person. This will still apply at all time points for those individuals who are unlikely to regain capacity and for those patients in hospital who are sedated/ventilated due to their COVID-19 symptoms, who may regain capacity. For those patients, capacity will always be assessed by a member of their direct clinical care team, the nurse in charge/manager in the nursing home and the PI at each hospital site who will be the consultant on or linked to the COVID ward (**The person assessing capacity will be recorded at all time points and a record kept**). For those that regain capacity during the duration of this research they will be given participant information sheet (appendix 4) to read for themselves and their consent (appendix 5) will be sought if they wish to proceed with the study. If they do not wish to continue, they will be given the option for any samples and data to be withdrawn and destroyed.

Sample Collection: Once informed consent has been obtained each participant will provide (i) one 30 ml whole blood sample, a saliva sample (~4ml) and one set of up to five 20ul dried blood spots (DBS; equivalent to five finger lancet blood droplets) and a lateral flow assay for COVID-19 antibodies performed at recruitment (between 0 and 10 days of symptom onset), (ii) again between 14-28 days after symptom onset (iii) again samples will be collected only if pneumonia occurs during episode (usually only in severe symptom cases) (iv) In addition, where possible samples will be collected at post 3 months, 6 months, 12 months and 18 months post symptom onset, the latter sample collections will take place at an agreed convenient time and place.

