Hospital and nursing home staff recruitment: All HSC employees aged 18 years and over, employed within facilities at the WHSCT, BHSCT and the SHSCT and trust affiliated nursing homes within the trust areas (n = 500) are eligible to participate in this research. Trust/nursing home wide emails with an attached PIS explaining the study (appendix 6) will be sent to all staff. In addition, information regarding the research will be put on Trust and Nursing home websites and social media platforms e.g. Facebook and Twitter. Posters (appendix 8) will also be placed in communal areas ensuring information can be accessed by everyone. Staff will be directed to the researchers on the study via email or phone to discuss the study in more detail. For those who still wish to participate and who meet the inclusion criteria, written informed consent (appendix 7) will be obtained by the researcher(s).

Sample Collection: Once informed consent has been obtained each participant will provide (i) one 30 ml whole blood sample, one set of dried blood spots (DBS) and a saliva sample (~4ml) at recruitment. Then, only if SARS-CoV-2 symptoms such as a high temperature/a

new continuous cough <https://www.nhs.uk/conditions/coronavirus-covid-19/check-if-you-have-coronavirus-symptoms/> experienced during 2 week post recruitment period: (ii) a saliva sample, one 30 ml whole blood sample and one set of dried blood spots (DBS) and a lateral flow assay for COVID-19 antibodies performed (between 0 and 10 days of symptom onset), (iii) a saliva sample, one 30 ml whole blood sample and one set of DBS and a lateral flow assay for COVID-19 antibodies performed between 14-28 days after symptom onset (iii) a saliva sample, one extra set of 30ml whole blood and DBS to be taken only if pneumonia occurs during (usually only in severe symptom cases) (iv) In addition, where possible sample will also be collected at 3 months, 6 months and 12 months of symptom onset. Sample collections will take place at an agreed convenient time and place.

Data Collection for all cohorts:

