The phenomic data collected will align with international/National data for phenotypic data collection (HDRUK). After informed consent (appendices 3, 5 & 7) is obtained by a member of the research team, participants will be asked to answer a health and lifestyle questionnaire at each timepoint (Appendix 9) that includes questions about their general medical and clinical history such as comorbidities, medications, respiratory illness, COVID-19 symptomatology, time to admission to hospital (if hospitalised) as well as lifestyle habits, family history etc.

-Missing information will be collected by the researchers by accessing the participants electronic care records or the participants medical notes provided they have consented for this option. Demographic variables in addition to age and gender will include height, weight and blood pressure will also be retrieved from the participants electronic care record. The researchers will have an honorary contract within the Health Trust(s) and will have approval and training to access and to use the patient care records. In case certain information is missing, the researchers will ask permission to follow up with the patient at a later time by phone. All medical records will be accessed on the Altnagelvin hospital site at C-TRIC and information will be manually inputted to a database on a university password protected and encrypted laptop.

Participants will also be asked whether they consent at each time point, to complete a validated mental health questionnaire, the General Health Questionnaire (GHQ-12), (appendix 10) to assess the association between their condition or perceived risk and their mental health and wellbeing. The researchers will arrange for completion of this questionnaire at a convenient time for the participant either on the day of recruitment, during the follow up visits, online or by phone.

-Participants also have the choice to consent to be contacted again to receive information regarding future studies.

Sample processing, storage and analysis

Saliva ~ 4ml will be collected in Oragene saliva collection kits (DNA Genotek), processed and analysed for COVID-19 genome sequencing and microbiome analysis.

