Whole blood samples and swab extract will undergo viral genome analyses sequencing, transcriptomics, epigenetics, single nucleotide polymorphism (SNP) genotyping, WGS and RNAseq generation. Sample analysis will be performed at NICSM by the researchers or by a third party such as the virology laboratories at Queens University Belfast (QUB), Regional Virus Laboratory Belfast (RVL), Olink® proteomics (Uppsala, Sweden) or Genomics Medicine Ireland (GMI, Dublin, Dublin). This will require aliquots of plasma/serum or DNA to be transferred to the approved third party proteomic or genomic or service providers (such as QUB, Olink or GMI). In this event, all samples will be pseudo-anonymised. The codes relating to participant identification will not be disclosed to this study partner and remain in the custody of the chief investigator. Third party providers have already been approved as service providers with satisfactory evidence of encryption in storage and transfer of data and appropriate Material Transfer, Confidentiality and Intellectual Property agreements signed off by both the third party and the University. Unused DNA or plasma which is analysed by a third party such as GMI or Olink® proteomics will be destroyed. The research organisations that will use samples or data derived from analysis of samples could be not-for-profit e.g. universities or for-profit commercial companies (such GMI). GMI, however, have agreed to undertake: SNP genotyping, WGS and RNAseq generation analysis at no cost. Participant's name, address and personal details will not be made available to any organisation beyond the study team

Inclusion criteria

All cohorts:

- Gender: Male and female
- Age: >18
- BMI: Any
- Ethnic origin: Any

Hospitalised, non-hospitalised and nursing home patients:

- Symptomatic/non-Symptomatic patients testing positive or suspected of being positive for COVID-19/SARS-CoV-2 by virus PCR assay
- Nursing homes caring for elderly residents
- COVID-19 wards of participating hospitals

Hospital and nursing home staff:

- Any member of hospital or nursing home staff are eligible to participate whether they have ever tested positive or not for COVID-19/SARS-CoV-2 by virus PCR assay even if non-symptomatic.

Exclusion Criteria***All cohorts:***

- Under 18 years of age
- Those with intellectual disabilities or mental health illness

Blood sample collection

All venous blood samples will be taken by a trained phlebotomist or member of the research clinical team.

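### Nursing home residents are recruited because they are PCR-positive or suspected, so objective (a)'s representative sample and the 60% prevalence estimate cannot be delivered as written

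*Protocol*

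**What the plan says.** **Aim.** Core objective (a) is to measure IgG in a sample described as representative of the Northern Ireland population at community (nursing home) level, and also in SARS-CoV-2 positive cases and frontline staff.

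**Sizing.** The Statistical Analysis section bases the sample size on infection prevalence in these groups. It assumes 20% in frontline staff (n = 246, or 295 with contingency) and 60% in hospitalised patients and nursing home residents (n = 369, or 443 with contingency). Each estimate is to lie within 5 points of the truth with 95% confidence.

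**Entry.** Phase 3 in the Study Design recruits patients from hospitals, nursing homes and the community who have tested positive by PCR. The section on hospital and nursing home patient recruitment likewise starts from COVID-19 positive patients and residents (n = 700). The Inclusion criteria admit patients and residents who test positive or are suspected positive. Staff may enter whatever their test status.

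**Exclusion.** Under the all-cohorts heading the protocol bars "Those with intellectual disabilities or mental health illness". Neither term is defined.

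**Consent.** The swab section and the patient recruitment section both provide nominated-person consent throughout follow-up. Both describe the people covered in these words: "for those individuals who are unlikely to regain capacity and for those patients in hospital who are sedated/ventilated due to their COVID-19 symptoms".

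**The concern.** A prevalence estimate needs a sample whose entry does not depend on the condition being counted. Here residents enter because they are known or thought to be infected. The resulting proportion describes how recruits were selected, not how common infection is in nursing homes. A reader who takes objective (a) and the 60% scenario at face value would apply the result to a population that was not sampled. The protocol says its findings could inform the regional exit from lock-down, so this matters.

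The exclusion narrows the sampled population further. It also leaves a smaller question: whether someone whose lasting incapacity comes from an excluded condition may enter through a nominated person.

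**Working it through.** **1. The plan's own figures.** The precision formula is n = z²p(1 − p)/d², with z = 1.96 and d = 0.05 (Statistical Analysis).

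- p = 0.20: 3.8416 × 0.16 / 0.0025 = 245.9, so 246; × 1.2 = 295.2, stated as 295.
- p = 0.60: 3.8416 × 0.24 / 0.0025 = 368.8, so 369; × 1.2 = 442.8, stated as 443.

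All four figures reproduce. The formula assumes that recruits are drawn from the target population without regard to infection status.

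**2. Whether that holds for patients and residents.** It does not. The Study Design and the recruitment section require a positive result, and the Inclusion criteria add suspected cases. No route is described for a resident who is neither positive nor suspected to enter this cohort. For staff there is no selection on test status, so the 20% scenario is not affected in this way.

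**3. What the sample would show.** Let c be the share of recruits who are PCR-confirmed and q the share truly infected among those only suspected. Treat confirmed recruits as infected. The infected share is then c + (1 − c)q. The protocol gives neither c nor q. As an illustration, set q to the planning value of 0.60, so the gap from 60% is 0.40 × c:

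| c (assumed) | Infected share | Gap from 60% |
|---|---|---|
| 0 | 60% | 0 points |
| 0.125 | 65% | 5 points |
| 0.50 | 80% | 20 points |
| 1 | 100% | 40 points |

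The last row is what the Study Design and recruitment wording imply. On this assumption the gap reaches the whole ±5-point margin once one recruit in eight is confirmed. With another q the gap changes. A result of 60% needs c + (1 − c)q = 0.60, hence c no greater than 0.60, and it would then reflect the mix recruited. A larger n changes none of this. The table concerns infection; IgG positivity may differ, because it also depends on when blood is taken.

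**4. Whether the retrospective samples fill the gap.** PCR-negative people do appear there. The waste-sample set is fixed at 200 negative and 200 positive for assay validation, so its positive share is 200/400 = 50% by design. The swab follow-up (about 500) draws on available extracts that tested positive or negative. Neither is a representative sample of nursing homes.

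**5. The exclusion.** Bias equals the share excluded multiplied by the difference in prevalence between excluded and included people. The protocol gives neither quantity, so no figure follows.

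**6. Consent route against exclusion.** The route names people unlikely to regain capacity separately from sedated or ventilated patients. The exclusion names two undefined groups, which may include some of the former. Incapacity due to sedation or ventilation is outside it.

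**The case against.** The protocol calls its aim preliminary data. Objective (a) lists its groups, some of them expressly positive cases, and the retrospective cohorts follow up people who tested negative. For the positive-case groups, selection on infection is intended, and that much stands. It does not rescue the nursing home part of the objective, which is the part called representative, or the 60% scenario, which covers hospitalised patients and residents together.

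A reader might infer that the nominated-person route flatly contradicts the exclusion. The document does not support that. The exclusion covers all cohorts, and the consent text sets a necessary condition, not a sufficient one: "The potential participant will not be enrolled on the study until full informed consent (appendix 14) has been given by the nominated person". The route keeps a purpose for sedated or ventilated patients and for other causes of incapacity. Nor does the lack of an eligibility condition in the nominated-person text single out that group: the waste-sample and swab sections state none for people who consent for themselves either. What remains is an unclear overlap.

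A reader might also infer that the exclusion biases the prevalence estimates, or that the mental health questionnaire and severity-model conclusions must be restricted because of it. No bias is shown, and restricting those analyses to eligible people is a defensible design choice. The point does not rest on either.

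**Conclusion.** The point holds for the patient and resident sample. As written, objective (a) and the 60% scenario describe a quantity that the entry rules cannot deliver. The sample sizes themselves are correct, and the staff scenario is not affected by selection on test status.

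The size of the distortion is not derivable. It runs from 0 to 40 points as the confirmed share goes from none to all, on the assumptions that suspected recruits are infected at the planned 60% and that confirmed recruits all count as infected. The conclusion that the sample is not representative does not depend on those assumptions.

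The exclusion narrows the population described, with an effect that is unknown and may be zero. The overlap with nominated-person consent is secondary and minor: a matter of clarity, of unstated extent, and possibly addressed in appendices that are not shown.

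**What to change.** 1. In objective (a), remove *representative* or qualify it to match how patients and residents are recruited.
2. In the Statistical Analysis section, state that the patient and resident estimate describes seropositivity among PCR-positive or suspected cases who meet the Inclusion and Exclusion Criteria, not community prevalence.
3. Reconcile the all-cohorts exclusion with the nominated-person text in the swab and patient recruitment sections. Define the excluded conditions and say whether people whose lasting incapacity comes from one of them may be enrolled. Which rule applies is for the sponsor and the ethics committee.

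The cost is a text amendment with ethics review, and possibly matching changes to the nominated-person documents. No sample size changes. The downside is a narrower stated target population.

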Study Design: This study will undertake: (a) the collection of retrospective waste plasma/serum samples from Covid-19 positive patients and extract from existing nasopharyngeal swabs and (b) the recruitment of Covid-19 positive hospitalised and non-

hospitalised and nursing home patients, hospital and nursing home staff, for whole genome sequencing, human host genomic analyses and viral genomic analyses. This research study will take place across three trust areas in Northern Ireland and will be conducted simultaneously in four phases, namely:

Phase 1- Rapid access of waste serum/plasma samples from hospital laboratories

Phase 2- Rapid access of nasopharyngeal swab extract, collected from patients, NHS and nursing home staff and members of the public.

Phase 3- Recruitment of SARS-CoV-2 patients who have tested positive by virus PCR assay from both hospitals and trust affiliated nursing homes and community.

Phase 4- Recruitment of hospital-tested and nursing home staff

Recruitment of participants and sample collection

Rapid Access to retrospective samples from hospital laboratories:

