When the participants agree to take part in a research study, the information about their health and care may be provided to researchers running other research studies in this organisation and in other organisations. These organisations may be universities, NHS organisations or companies involved in health and care research in this country or abroad. Participants' information will only be used by organisations and researchers to conduct research in accordance with the UK Policy Framework for Health and Social Care Research. This information will not identify the participants and will not be combined with other information in a way that could identify the participants. The information will only be used for the purpose of health and care research, and cannot be used to contact the participants or to affect their care. It will not be used to make decisions about future services available to the participants, such as insurance.

Statistical Analysis

A statistical sample size calculation was based on the core objective of measuring SARS-CoV-2 infection prevalence in specified populations: at community level (nursing home), in hospitalised SARS-CoV-2 positive cases and in frontline healthcare staff. If the true

prevalence of COVID-19 in frontline staff is 0.20 (20%), with a sample size of $n = 246$ we are 95% confident that our estimate will not be more than 5% (desired precision) below or above the true prevalence (20%). If we add 20% contingency in sample size for loss of follow up or drop out, we estimate that $n = 295$ frontline staff from each setting would be required. In another scenario, If the true prevalence of COVID-19 in hospitalized patients and nursing home residents is 0.60 (60%), with a sample size of $n = 369$ we are 95% confident that our estimate will not be more than 5% below or above the true prevalence (60%). Again, allowing for 20% contingency, we estimate that $n = 443$ patients from either setting are required.

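### The patient and nursing-home cohorts are sized to estimate infection prevalence, but hospital patients are enrolled because they are PCR-positive or suspected, so their observed proportion cannot be prevalence; for residents the rule is ambiguous

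*Protocol*

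**What the plan says.** The first paragraph of Statistical Analysis derives the sample size from one aim, given as "measuring SARS-CoV-2 infection prevalence in specified populations: at community level (nursing home), in hospitalised SARS-CoV-2 positive cases"; staff on the front line are the remaining group. For the second scenario it supposes that the true "prevalence of COVID-19 in hospitalized patients and nursing home residents is 0.60 (60" per cent), and concludes that 369 participants give an estimate within 5 points with 95% confidence. Adding 20% gives 443 from either setting.

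Other sections define who these people are:

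- Study Design, Phase 3: "Recruitment of SARS-CoV-2 patients who have tested positive by virus PCR assay from both hospitals and trust affiliated nursing homes and community".
- Hospital and nursing home patient recruitment: "COVID-19 positive/ SARS-CoV-2 inpatients and non-hospitalised patients (n = 700) aged 18 years and over". Inpatients are those admitted to COVID-19 wards, including intensive care. The sentence continues "or out-patient and residents of trust affiliated nursing homes will initially be approached by their clinician".
- Inclusion criteria, patient heading: the first bullet sets the infection status, "Symptomatic/non-Symptomatic patients testing positive or suspected of being positive for COVID-19/SARS-CoV-2 by virus PCR assay". The second bullet names the type of home and mentions no test: "Nursing homes caring for elderly residents". The third bullet limits where inpatients are found: "COVID-19 wards of participating hospitals".
- Inclusion criteria, staff heading: staff may join whatever their PCR history.

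Objective (a), under Overall Purpose/objectives, is to measure IgG. It describes the nursing-home sample as representing the Northern Ireland population at community level.

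**The concern.** A prevalence is estimated from people sampled without regard to whether they have the condition. Here the condition, or suspicion of it, is the entry criterion for hospital patients. The sizing sentence shows the problem by itself: infection prevalence among positive cases is 100% by definition, yet the planning value is 60%.

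The overall purpose includes preliminary prevalence data, and the introduction says the study could inform the exit from lockdown. A proportion fixed by recruitment, reported as prevalence with a margin of 5 points, would give false assurance for that use. Analysis cannot undo selection on the quantity being estimated, so this cannot be left to a later statistical plan.

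**Working it through.** **Inputs.** From Statistical Analysis: p = 0.60 for patients and residents, p = 0.20 for staff, d = 0.05, 95% confidence (z = 1.96), contingency 20%. From patient recruitment: n = 700.

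**1. The plan's own figures.** n = z² p(1−p) / d².

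- Patients and residents: 1.96² × 0.60 × 0.40 / 0.05² = 368.8, so 369; 369 × 1.2 = 442.8, so 443. Both match.
- Staff: 1.96² × 0.20 × 0.80 / 0.05² = 245.9, so 246; 246 × 1.2 = 295.2, so 295. Both match.

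The arithmetic is sound. It presumes sampling that does not depend on infection status.

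**2. What the hospital cohort would yield.** Let f be the share enrolled as PCR-confirmed and q the true positivity among those enrolled as suspected. The observed infection proportion is f + (1−f)q. The protocol gives neither f nor q, so these are illustrations, with q running from 0.1 to 0.6:

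| f (assumed) | Observed proportion |
|---|---|
| 1.00 (Phase 3 rule) | 1.00 |
| 0.90 | 0.91 to 0.96 |
| 0.75 | 0.775 to 0.90 |
| 0.50 | 0.55 to 0.80 |
| 0.25 | 0.325 to 0.70 |
| 0 | 0.10 to 0.60 |

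The result is driven by whom the study chooses to enrol. A value of 60% can occur, but it would describe the recruitment mix.

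**3. Residents.** Phase 3 and the first patient bullet of the Inclusion criteria require positive or suspected status. The nursing-home bullet and the residents clause in the recruitment section carry no explicit PCR condition. On the first reading the problem is the same as for inpatients. On the second, a resident proportion could be estimated.

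**4. Could another phase supply the estimate?** Phase 1 waste samples are set at 200 PCR-positive and 200 PCR-negative by design, and follow-up reaches those who are contactable and consent. Phase 2 starts from people already swabbed, with no stated sampling rule. Neither is an unselected sample.

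**5. Precision if the target becomes IgG positivity.** Half-width = 1.96 × √(p(1−p)/n), independent observations:

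- n = 369: 5.1 points at p = 0.50, 5.0 at 0.60, 4.1 at 0.80, 3.1 at 0.90.
- n = 700, all pooled with a result: 1.96 × √(0.25/700) = 3.7 points at p = 0.50.

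**6. Fit with recruitment.** If 443 is a pooled requirement, it fits within 700. If it is per setting, 2 × 443 = 886 does not fit.

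**The case against.** The best defence is that prevalence is a loose word for seropositivity. The sizing paragraph invokes a core objective, and the one that names these populations is objective (a), which measures IgG. On that reading 0.60 is the planned seropositive proportion, and PCR-positive participants sampled within 10 days of onset could well be antibody-negative. This stands as a possible intention, but not as a reading of the text, which speaks of infection prevalence and prevalence of COVID-19. IgG positivity in known cases is a seroresponse proportion. It depends on sampling time, and Sample Collection runs from 0–10 days to 18 months after onset with no time named for this estimate.

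It is also fair to say that the output is called preliminary, that 369 can survive the repair, and that most of the repair is rewording. That limits the cost. It does not make the present target estimable.

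Four stronger readings are tempting but unsupported:

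- A reader might infer that 60% requires 40% of those analysed (0.40 × 369, about 148) to be uninfected. That holds only if prevalence means infection, not under the IgG reading.
- A reader might infer that no resident prevalence can be obtained. The text on residents is ambiguous, so this is not established.
- A reader might infer that the sample is too small because residents cluster within homes. The protocol gives no clustering figure, and that reason does not extend to inpatients. Only the direction, wider intervals, can be stated.
- A reader might infer that the whole prevalence purpose fails. Staff are eligible whatever their PCR status, so it does not.

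**Conclusion.** The point holds firmly for hospital patients: the stated precision, 5 points either side of 60%, belongs to a quantity that this recruitment cannot estimate. If all are PCR-positive, the observed infection proportion is 100%. If suspected cases are included, it reflects the confirmed/suspected mix. For residents the finding is an unresolved ambiguity, and their prevalence is inestimable only if the positive-or-suspected rule applies to them. The description of the nursing-home sample as representing the Northern Ireland population is unsupported on either reading.

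The sample sizes are not miscalculated. The conclusion rests on the eligibility text alone; the values of f and q only illustrate it. The half-widths assume independent observations and an IgG result for every participant counted. The staff figures (246 and 295) are untouched by this selection, although those taking part are volunteers responding to emails, posters and online notices.

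**What to change.** In this order:

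1. Reconcile Study Design (Phase 3), the patient recruitment section and the Inclusion criteria. State, separately for patients and residents, whether they must be PCR-positive, may be suspected, or are enrolled whatever their status. State also whether the 443 is pooled or per setting.
2. In Statistical Analysis, restate the hospital-patient target as the proportion IgG-positive among PCR-confirmed participants at one named sampling time, with its own planning proportion. Keep n = 369 with an IgG result and give the half-width as at most 5.1 points if observations are independent (3.7 at p = 0.50 if all 700 are pooled), noting that it widens if residents cluster within homes. Apply the same restatement to residents unless step 1 establishes that they are enrolled regardless of PCR status.
3. Make no inpatient or Northern Ireland community prevalence claim from the patient cohorts, and none for residents unless they are enrolled regardless of status. Remove from objective (a) the claim of community-level representativeness. Keep the staff estimate, described as coming from volunteers.

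These changes need no additional participants or samples. The cost is that the sponsor gives up the inpatient and community prevalence claim, which is part of the stated purpose. Keeping an inpatient prevalence claim would mean enrolling inpatients regardless of PCR status, which is a change of design.
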